Interventions designed to improve metabolic health and increase lean body mass in obese patients with high levels of visceral adiposity may restore myocardial mechanics and reduce the future risk of developing HF. Exercise training in particular can be an effective means of improving cardiac function in obesity with small studies showing improvements in LV longitudinal strain, diastolic function and reductions in indexed LV mass. Designing an exercise program that specifically targets metabolic parameters and reduces visceral adiposity may be more effective in reversing cardiovascular abnormalities associated with abdominal obesity than traditional aerobic exercise alone.

To supplement exercise training, we also propose adding high dose (2 grams/day) omega-3 PUFA to aid in metabolic remodeling. PUFA, administered in the form of fish oil, can increase fatty acid oxidation, increase lean body mass while decreasing fat mass. When combined with moderate aerobic exercise, PUFA can potentiate fat mass loss and decrease triglyceride/HDL-c ratios. Complementing HIIT with daily omega-3 PUFA administration may improve body composition and cardiovascular remodeling than either intervention alone.

The primary objective of this application is therefore to identify middle aged (age 40 – 60), sedentary, obese individuals with high levels of visceral adiposity (>2.5 kg), elevated biomarkers of cardiac injury (high sensitivity troponin) or wall stress (NTBNP), and initiate an exercise program designed to reduce visceral fat content and regress myocardial triglyceride accumulation. We hypothesize that modulating metabolic parameters associated with adverse cardiac remodeling will improve LV structure and function by an approach that is not necessarily predicated on weight loss. After this aim is accomplished, we will have established a novel approach to reversing diastolic and vascular abnormalities associated with obesity which may ultimately lead to HFpEF prevention in a high risk population. Such a determination would have enormous public health significance since this condition is quite difficult to treat once established.

Concise Summary of Project:

Experimental Design and Methods:

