To test the hypothesis that reduction in myocardial triglyceride content will improve markers of diastolic function, we have designed a randomized, double blind, placebo controlled trial. To recap, we will study four groups of previously sedentary obese middle aged subjects at high risk for development of HF for one year with the following interventions: A) sedentary controls taking placebo; B) sedentary subjects taking omega-3 fatty acids; C) subjects undergoing high intensity aerobic exercise training while on placebo and D) subjects undergoing high intensity aerobic exercise training while taking omega-3 fatty acids. We anticipate the combination of high intensity aerobic exercise in conjunction with high dose omega-3 supplementation will reduce visceral adiposity, decrease myocardial triglyceride content and improve markers of diastolic and vascular function.

We will need to complete baseline testing on 80 subjects to enter the 1 year intervention with 44 assigned to exercise and 36 to yoga control. This difference is designed to account for differences in compliance within the 2 exercise groups. Within each exercise/yoga group, half of subjects will be randomized to placebo or omega-3 fatty acid supplementation. For the exercisers, 22 subjects will be given placebo and 22 will be given omega-3. For the yoga control, 18 will receive placebo and 18 will receive omega-3. Ultimately the study is powered to end up with 15 subjects per group (total N=60) accounting for drop outs to complete all follow up testing (please see “power calculations” section on page 697 (of 731) of the AHA grant, submitted as “protocol” which develops and supports these numbers in some detail).

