The dosage of omega-3 supplementation will be 2 grams once daily and provided in the form of prescription strength Lovaza, a commercially available pharmaceutical used in the treatment of hypertriglyceridemia. Typical dosage for Lovaza in clinical use is 4 grams daily or divided twice daily. We have chosen 2 grams once daily on the basis of prior studies using omega-3 to improve lean body mass and fatty acid oxidation rates. Omega-3 fatty acids are a commonly used over-the-counter supplement and in numerous clinical trials have been shown to be safe with minimal side effects. Please see “potential risks” section for more detail regarding drug safety profile. For patients assigned to placebo, an identical appearing gel capsule containing olive oil will be given in a dosage of 1 gram daily.

Study Procedures:

Five subjects, enrolled using an abbreviated informed consent, will participate in testing the MRI protocol developed for the primary study.

Overview: Once a subject has enrolled in our study, he or she will undergo a comprehensive set of “Baseline Testing”, one year of the experimental intervention (i.e. randomization into one of

the groups as described above) and a comprehensive set of “Follow-up Testing” at the conclusion of the intervention. The “Experimental Intervention” has been described in detail in the STUDY DESIGN section of this document and will be briefly reviewed below. The “Baseline Testing” and “Follow-up Testing” protocols are similar and are described in detail below.

“Baseline Testing” Procedure: The baseline testing procedure begins with a screening visit. If all inclusion criteria are met and no exclusion criteria are identified, the subject will be given the option to enroll in the study. After enrolling in the study, additional demographic information is obtained and Study Day 1, Study Day 2, and Study Day 3 are scheduled.

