As this study is sponsored by the AHA and passed peer review, the biostatistics section is omitted per instructions, but is available in the full protocol. (page 697 of 731 of the AHA grant). Briefly, the primary outcome of interest is reduction in myocardial triglyceride content by MRI spectroscopy. Secondary outcome measures are LV concentric remodeling and diastolic function. The sample size for the study was calculated using a two factor factorial design which provides adequate power to detect a main effect (99%) as well multiple comparisons between individual groups (80%).

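### Omega-3 is dosed at 2 g daily but its look-alike placebo at 1 g daily, so the written regimens do not support the double blind

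*Protocol*

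**What the plan says.** The paragraph on supplementation in the protocol's Study design section gives both regimens. For the active arm: "The dosage of omega-3 supplementation will be 2 grams once daily and provided in the form of prescription strength Lovaza". The same paragraph defends that dose: "We have chosen 2 grams once daily on the basis of prior studies". The Background section agrees: "we also propose adding high dose (2 grams/day) omega-3 PUFA to aid in metabolic remodeling". For the placebo arm there is a single statement: "an identical appearing gel capsule containing olive oil will be given in a dosage of 1 gram daily". No reason is given for the lower amount.

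On blinding, the Study design section says "we have designed a randomized, double blind, placebo controlled trial". The Specific Aim and the Experimental Design and Methods sections describe the trial in the same terms, and the Potential Risks section repeats the claim when it discusses omega-3. On allocation, the Study design section says "Within each exercise/yoga group, half of subjects will be randomized to placebo or omega-3 fatty acid supplementation". The Biostatistics section says that "the primary outcome of interest is reduction in myocardial triglyceride content by MRI spectroscopy". The SAP does not mention capsule dose.

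**The concern.** A placebo that resembles the active product capsule for capsule conceals allocation only if the daily regimen also matches. Here the appearance is matched on paper and the daily amount is not.

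This matters because the drug factor has to carry the double-blind claim. Participants know whether they were assigned to interval training or to yoga, so they can be blinded only to omega-3 versus placebo. The active dose is written in the protocol. Anyone who knows it and learns how many capsules a subject takes could work out the arm. The trial is single-site, exercisers work closely with an assigned physiologist, and all subjects are monitored for adverse reactions, so such contact is plausible.

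An MRI spectroscopy measurement is not very open to participant expectation. Other parts of the trial are more exposed. Maximal exercise testing depends on effort. The SAP's per-protocol analysis keeps only subjects who completed at least 80% of the prescribed training, so knowledge of allocation could affect who is analysed. Separately, a 1 g placebo leaves the arms unmatched on oil load, while gastrointestinal distress is one of the monitored reactions.

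**Working it through.** No sample-size, power or alpha figure is in question. The SAP's inputs (0.9% falling to 0.45%, SD 0.4%, alpha 0.05, power 80%) do not involve the placebo dose. The check compares the two regimens.

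**Inputs**

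| Item | Value | Where |
|---|---|---|
| Omega-3 daily dose | 2 g | Protocol, Study design (stated twice) and Background (once) |
| Placebo daily dose | 1 g | Protocol, Study design (once) |
| Capsule strength or daily count | not stated | neither document |
| Planned subjects, exercise | 22 omega-3, 22 placebo | Protocol, Study design |
| Planned subjects, yoga | 18 omega-3, 18 placebo | Protocol, Study design |

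**Step 1: ratio of daily amounts.** 2 g / 1 g = 2.

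**Step 2: capsules per day.** Capsules per day = daily dose / fill per capsule. Assume the same fill *s* in both arms. The ratio of counts is (2/*s*) / (1/*s*) = 2, whatever the value of *s*. The strengths below are illustrative:

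| Fill per capsule, both arms | Omega-3 per day | Placebo per day |
|---|---|---|
| 0.5 g | 4 | 2 |
| 1 g | 2 | 1 |
| 2 g | 1 | 0.5 (not practical for a gel capsule) |

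**Step 3: what would equalise the counts at the written doses.** The placebo fill would have to be half the active fill: 0.25 g against 0.5 g, 0.5 g against 1 g, or 1 g against 2 g. Neither document describes such a capsule. The counts would then match, but the daily oil would still be 2 g against 1 g.

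**Step 4: who is affected.** Omega-3: 22 + 18 = 40. Placebo: 22 + 18 = 40. Total: 80. This is the number of subjects under the mismatched instruction, not an effect size.

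**Step 5: after correction.** With placebo at 2 g in the same capsule, the ratio is 2/2 = 1 and the counts are equal.

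**The case against.** The strongest reply is that this is a slip of wording. The placebo sentence speaks of a single capsule and attaches 1 g to it, which fits a capsule size written as a daily dose. On that reading both arms may in practice take the same number of capsules, and nothing in the conduct of the trial is wrong. This reading is plausible and cannot be excluded. It does not rescue the text, because that sentence is the only placebo dosing instruction in the documents.

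Second, matching in outward appearance does not imply equal fill, so the 2:1 count is an inference. This stands as a limit. The documented fact is 2 g against 1 g, and the count difference follows only if the fill is the same in both arms.

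Third, the protocol points to a longer grant document that might contain capsule details. Those pointers concern power and biostatistics. For the intervention, the Study Procedures and Experimental Intervention text sends the reader back to the Study design section, where the mismatch lies.

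Fourth, no harm is demonstrated. Each participant sees only one regimen, the documents do not say who handles or counts capsules, and nothing suggests that those reading the spectroscopy would know the counts. All of this is correct. It limits how strongly the point can be put, but it does not remove the inconsistency.

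**Conclusion.** The point holds: the placebo regimen is wrong as written. The stated daily amounts differ by a factor of 2, with three statements of 2 g for omega-3 against one of 1 g for placebo. A 2:1 difference in daily capsule count follows if fill per capsule is equal, and that is an assumption. Whether the blind would be broken in practice is not established, and the size of any bias cannot be estimated from the documents. The text should be corrected because it bears directly on the double-blind claim for one of the two randomised factors. Confidence is moderate, mainly because a drafting error is a credible explanation.

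**What to change.** State the placebo in the Study design section as 2 g of olive oil once daily, with the same number, size and appearance of capsules on the same schedule as omega-3. If 1 g is the capsule size, write two 1 g capsules once daily for both arms. Before capsules are dispensed, confirm the matched regimen with whoever dispenses them, since the documents do not name that party.

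The cost is one line of protocol text and one check, plus possibly more placebo supply if 1 g a day was in fact what had been ordered. Sample size and analysis are unaffected.

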The primary objective of this project, which reflects specific aim 2 of Drs. [name]/[name]'s AHA grant, is therefore to identify high risk, sedentary, middle aged obese individuals with high visceral fat levels, and initiate an exercise program in conjunction with omega-3 fatty acid supplementation designed to reduce visceral adiposity and regress myocardial triglyceride accumulation. Findings from this aim would have enormous public health significance and establish a novel, practical exercise training program and “nutri-ceutical” strategy to reverse obesity related cardiovascular remodeling.

Hypothesis:

High aerobic exercise training in conjunction with daily omega-3 supplementation will reduce visceral myocardial triglyceride accumulation by reducing visceral adiposity. A reduction of myocardial fat will lead to improved LV structure and diastolic function by an approach that is not necessarily predicated on weight loss.

Specific Aim:

To test our hypothesis that reduction in myocardial triglyceride content will improve markers of

diastolic function, we have designed a randomized, double blind, placebo controlled trial. We will study four groups of previously sedentary obese middle aged subjects at high risk for development of HF for one year with the following interventions: A) sedentary controls taking placebo; B) sedentary subjects taking omega-3 fatty acids; C) subjects undergoing high intensity aerobic exercise training while on placebo and D) subjects undergoing high intensity aerobic exercise training while taking omega-3 fatty acids. Subjects will be categorized as high risk and enrolled on the basis of elevated serum biomarkers (cTnT) and high visceral fat content (>2.5 kg). We will perform comprehensive non-invasive assessments of cardiovascular structure and systolic/diastolic function before and after 1 year of an exercise intervention involving high intensity intervals and omega-3 administration. We anticipate the combination of high intensity aerobic exercise in conjunction with high dose omega-3 supplementation will reduce visceral adiposity, decrease myocardial triglyceride content and improve markers of diastolic and vascular function.

Background:

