“Baseline” Screening Procedure: To determine whether a subject has interest and is eligible for our study, the first visit will be dedicated to screening. During this visit, we will obtain: informed consent, a medical history and physical exam, a screening electrocardiogram and a screening echocardiogram. Furthermore, we will begin the process of obtaining additional demographic data including: a) 24 hour ambulatory blood pressure monitor to most precisely measure baseline blood pressure and its circadian variability; and b) routine blood work (serum chemistries). This visit will usually last between 2-2.5 hours; it involves one blood draw of approximately 4 tablespoons.

In addition to the screening visit described above, each subject will go through a standard protocol consisting of 3 days of testing, separated by at least 72 hrs, but no more than 4 wks between tests:

“Baseline” Day 1: This visit consists primarily of a maximal exercise test and a screening echocardiogram with the measurement of echo derived wall motion and systolic volumes, blood pressure, ECG, heart rate, oxygen uptake, cardiac output (acetylene rebreathing method), stroke volume, total peripheral resistance, and a-vO₂ difference. Goals of this day are to: 1) estimate the peak VO₂ and 2) carefully assess for the presence of provable ischemia via both ECG and contractile imaging. This visit will usually last between 1.5 - 2 hours; no blood draws are performed during this visit.

“Baseline” Day 2: This visit consists of three different studies. It will last approximately 4.5 hours.

- 1) Submaximal and maximal exercise test: Measurements of blood pressure, ECG, heart rate, oxygen uptake, cardiac output (acetylene rebreathing method), stroke volume, total peripheral resistance, and a-vO₂ difference will be done during the exercise test. Goals of this day are to: 1) quantify the augmentation of SV during submaximal exercise, 2) precisely measure the VO_{2max}; and 3) determine the relationship between cardiac output. There are no blood draws performed during this study; however, 3 fingersticks are performed to measure lactate at various stages of the submaximal and maximal exercise testing.

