- 2) Arterial compliance testing: Used to determine the flexibility of the arteries. We will obtain blood pressure measurements through several different non-invasive techniques and take pictures of the arteries using ultrasound. The arteries that we will examine include the arteries in the wrist, elbow, neck, groin, and stomach. We will also collect approximately 4 tablespoons of blood to measure serum biomarkers of cardiac and metabolic health.
- 3) Body composition analysis: Used to determine the body's muscle, fat, and water composition using skin caliper technique and underwater weighing techniques. First, we will obtain detailed measurements of height, weight, skinfold thickness, etc., using measuring tape and calipers. There is no risk with this procedure, though some individuals experience some pinching from the calipers. We will also measure body composition using DEXA scanning. There is very low dose radiation associated with the

scan, about 1/10th the dose of an x-ray. Prior to a DEXA, we will perform a routine pregnancy test to ensure that subjects are not pregnant before undergoing the scan.

“Baseline” Day 3: Magnetic Resonance Imaging - The 3rd day is devoted to MRI, and includes measurements of LV mass, aortic compliance, MR spectroscopy for the assessment of myocardial triglyceride concentration, and delayed enhancement imaging for quantification of fibrosis. We have developed an integrated protocol which starts with the anatomic images for measurements of cardiac and vascular morphology followed by spectroscopy for triglyceride content. This visit will usually last between 3-4 hours; no blood draws are performed during this visit.

Experimental Intervention:

The experimental intervention involves randomization into one of four groups. This randomization is designed to assess the impact of omega-3 fatty acids and high intensity aerobic exercise training versus placebo. A more detailed description of the “Experimental Intervention” is included in the STUDY DESIGN section of this document.

“Mid Progress Testing” Procedure: At 6 months into the experimental intervention, subjects will return to the lab for mid-progress testing. This day is identical to “baseline day 2” and allows us to gauge adequacy of the exercise training intervention as well as to assess changes in body composition.

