“Follow-up Testing” Procedure: At the conclusion of the one year experimental intervention, follow-up testing will be performed to assess the effects of the intervention. The “Follow-up Testing” protocol is similar to “Baseline Testing” with the omission of the “Baseline” Screening Procedure and “Baseline” Study Day 1.

“Follow-up” Day 1: This day is identical to “Baseline” Day 2 with the additional measurement of 24 hour ambulatory blood pressure.

“Follow-up” Day 2: This day is identical to “Baseline” Day 3.

At the conclusion of the “Follow-up Testing”, each subject will have completed our study and reimbursement will be distributed.

Regarding the storage of blood samples, we will retain whatever blood is left over after all the analyses are complete in case other blood tests become available that might be useful to explain the effects of aging and obesity on the heart. The samples will be kept in the freezer in the biochemistry lab at the IEEM with a code to specify from which patient it comes and the study date. Only the Principal investigator and biochemistry lab staff will have access to these samples.

Criteria for Inclusion of Subjects:

One hundred twenty healthy, sedentary men and women ages 40-60 will be recruited to start the intervention on 80 who complete all baseline testing. The key inclusion and exclusion criteria are as detailed in the SUBJECT POPULATION section above. To recap, subjects will be recruited based on 1) the presence of high visceral adiposity (>2.5 kg) assessed by either MRI or DEXA scan, 2) a normal ejection fraction ($>50\%$); 3) elevated serum biomarkers of sub-clinical cardiac injury (cardiac troponin T, brain-type natriuretic peptide) and 4) obesity with BMI range $30 - 50$ kg/m^2 . Subjects will be recruited from the DHS and CCLS without regard to race or gender.

Criteria for Exclusion of Subjects:

Exclusion criteria include age < 40 or > 60 , body mass index > 50 , $< 30 \text{ kg}/\text{m}^2$ and any history of insulin dependent diabetes, heart failure, myocarditis, restrictive cardiomyopathy, permanent/persistent atrial fibrillation, severe chronic obstructive pulmonary disease, unstable coronary artery disease or recent (<12 month) acute coronary syndrome, cerebrovascular disease as evidenced by prior transient ischemic attack or stroke and active/recent tobacco use (quit < 5

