years). Female patients will be excluded if they are pregnant or plan to become pregnant (expected rare occurrence in the selected age range of 40 – 60). Patients will be excluded if they are taking non-statin lipid lowering agents (fibrates, niacin, or fish oils) or are unable to exercise. Subjects will also be excluded if they have any contra-indications to MRI including heart pacemaker/internal cardiac defibrillator, heart valve replacement, aortic clips, any metal fragments in the body, brain clips or pieces of metal used in brain surgery, pieces of metal in the body resulting from work as a sheet-metal worker or welder, clips placed in an internal organ, prosthetic devices, such as middle ear, eye, joint, or penile implants, joint replacement, a hearing aid that cannot be removed, an insulin pump, an intrauterine device (IUD), a shunt or stents, a metal mesh or coil implants, metal plate, pin, screws, or wires, or any other metal implants. Subjects unable to speak English will not be recruited because of the complex experimental studies and the need for precise communication between the volunteers and the research staff to ensure safety. All subjects will undergo stress testing as part of screening and if provable ischemia is detected, they will be referred to their primary physicians for appropriate follow-up.

Sources of Research Material

Research material will consist of paper, tape, and computer records of physiological signals, as well as echocardiographic images stored on electronic media. For subjects who are referred from the Dallas Heart Study, we receive demographic information including name, age, date of birth, phone number, etc. All data is obtained exclusively for research purposes and will be filed in locked cabinets in the PI's laboratory.

Recruitment Methods and Consenting Process:

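### Does dropping the echocardiogram visits at follow-up leave the secondary outcome of diastolic function without a 1-year value?

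*Protocol*

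**What the plan says.** The Specific Aim section of the protocol makes a paired commitment: "We will perform comprehensive non-invasive assessments of cardiovascular structure and systolic/diastolic function before and after 1 year of an exercise intervention". The Biostatistics section names diastolic function as a secondary outcome without giving a parameter or modality, although it does give the modality of the primary outcome (MRI spectroscopy). The SAP, under Power Calculations, lists diastolic strain among the variables for a mixed model repeated measures analysis, again without a modality.

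Under Study Procedures, echocardiography appears at two baseline visits. The screening visit has "a screening electrocardiogram and a screening echocardiogram". Baseline Day 1 has "a screening echocardiogram with the measurement of echo derived wall motion and systolic volumes". Baseline Day 2 involves ultrasound only to "take pictures of the arteries using ultrasound". Baseline Day 3 is the MRI visit, which "includes measurements of LV mass, aortic compliance, MR spectroscopy for the assessment of myocardial triglyceride concentration, and delayed enhancement imaging for quantification of fibrosis".

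Follow-up testing repeats the baseline set "with the omission of the “Baseline” Screening Procedure and “Baseline” Study Day 1". Follow-up Day 1 repeats Baseline Day 2 and adds ambulatory blood pressure. Of Follow-up Day 2 the protocol says: "This day is identical to “Baseline” Day 3".

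Sources of Research Material mentions physiological records "as well as echocardiographic images stored on electronic media" and does not mention MRI images.

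**The concern.** Diastolic function is not a peripheral outcome here. The hypothesis is that lowering myocardial triglyceride improves it, so a trial that measured it only at baseline could not test the second half of its own argument. The visit plan invites that worry. Every listed echocardiogram sits in a visit that is dropped at follow-up, the only imaging named as research material is echocardiographic, and the list of MRI measures does not mention diastolic function or strain.

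If echocardiography were the intended source, following the plan would leave the SAP's repeated measures model with no post-intervention value for this outcome. An image not acquired at the final visit cannot be recovered later. That would be a serious loss for a secondary outcome, although the primary outcome would stand.

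**Working it through.** No figure in the plan is in dispute, so the check is a visit-by-visit inventory followed by a comparison of the relevant sections.

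**Cardiac imaging by visit** (protocol, Study Procedures)

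| Visit | Echocardiogram | Cardiac MRI |
|---|---|---|
| Baseline screening | listed | no |
| Baseline Day 1 | listed | no |
| Baseline Day 2 | no (arteries only) | no |
| Baseline Day 3 | no | listed |
| 6-month visit (same as Baseline Day 2) | no | no |
| Follow-up Day 1 (Baseline Day 2 plus ambulatory blood pressure) | no | no |
| Follow-up Day 2 (same as Baseline Day 3) | no | listed |

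Echocardiograms: 1 + 1 = 2 before randomization and 2 − 2 = 0 after it. Cardiac MRI: 1 before and 1 after. MRI is the only cardiac imaging that can give a within-subject change under the plan as written.

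**What the echocardiograms are for.** Both carry the word screening. The Day 1 study is specified for wall motion and systolic volumes, and the goals of that day are an estimate of peak oxygen uptake and a search for ischemia by ECG and contractile imaging. The exclusion criteria section likewise treats stress testing as part of screening. No section attaches a diastolic measure to either study. Leaving out eligibility and ischemia checks a year later is ordinary design.

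**What points to MRI.**
- Compensation for Subjects describes both baseline and follow-up testing as cardiac MRI, body composition and exercise tests. Echocardiography appears in neither description.
- The SAP names diastolic strain together with LV mass index and LV concentricity index. LV mass is an MRI Day 3 measurement in the protocol, so at least one companion variable comes from that scan.
- Study Procedures says that an MRI protocol was developed for the main study and tried out on five subjects, and the Day 3 text calls it integrated.
- The Specific Aim requires values before and after. Read together with the follow-up schedule, only MRI meets that requirement.

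**What the storage sentence shows.** It names echocardiographic images, which the two baseline studies explain fully. It also leaves out MRI images, although MRI supplies the primary outcome. It cannot be a complete list of outcome sources, so it says nothing about which modality gives the diastolic measure.

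**The case for a change.** The strongest reply is that the MRI reading is itself an inference. The Day 3 list names LV mass, aortic compliance, spectroscopy and delayed enhancement, and no diastolic or strain measure. Nothing states that diastolic function in the protocol and diastolic strain in the SAP are the same variable. Staff working only from this text would have to guess the source of a named secondary outcome. A strain acquisition left out of the baseline scan would be as unrecoverable as an echocardiogram left out at the end. One sentence would remove the doubt.

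Part of this stands: the supplied documents do not state the parameter or the modality. But the Day 3 list opens with a word that marks it as non-exhaustive, and the SAP introduces its variables as examples. The protocol is a project summary whose Biostatistics section says that the full text is in the grant, and the SAP is a short extract. Silence in such documents does not show that the acquisition is undefined. The serious consequence, a missing 1-year value, arises only if echocardiography is the intended source, and no text says so.

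**Conclusion.** No change to the plan is called for. The observation about the visits is accurate: 2 of 2 listed echocardiograms fall in visits that are not repeated. It describes screening tests being left out of follow-up, not an outcome being lost. Followed as written, the schedule gives one cardiac MRI before and one after the intervention for each subject who completes testing, and nothing in the documents shows that the diastolic measure comes from anywhere else. Adding a follow-up echocardiogram would be an extra procedure resting on a reading that the text does not establish.

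What is left is missing detail of a kind that the imaging team and analysts fill sensibly: the name of the diastolic variable and the statement that it comes from the Day 3 and Follow-up Day 2 scans. Writing that down would be tidy, but it would alter no visit, analysis or result.

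This rests on one assumption, that the MRI protocol includes a diastolic or strain acquisition at both times. The documents support it by inference and do not state it. The primary outcome does not depend on it, because spectroscopy is listed at baseline and the follow-up scan is declared identical.
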